8.3. Aim-Specific Plans

Plans for Aim 1 (PRIMARY).

Treatment response will be calculated as the depression (HDRS) scores from pre- to post-treatment. A two-way analysis of variance (ANOVA) will be performed using within-participant factor of time (before or after treatment), between-participant factor stimulation type (delta-beta tACS, active-sham), and the interaction between time and stimulation type. We hypothesize to find an interaction between time and stimulation type. Post hoc differences will be investigated. We hypothesize that the predicted interaction will be driven by a decrease in depressive symptoms for delta-beta tACS compared to the active-sham. Sensitivity analyses will be conducted to evaluate the specificity of these effects: a similar analysis with anxiety symptoms as the dependent variable and we do not expect that delta-beta tACS will have any effect on anxiety symptoms.

Further, we will conduct exploratory generalized linear mixed models will be conducted to examine potential confounds on treatment effect (e.g., age, sex, baseline depressive symptoms).

Plans for Aim 2 (SECONDARY).

Delta-beta phase amplitude coupling will be calculated between the phase of delta oscillations (2-3 Hz) in prefrontal electrodes (FCz and surrounding electrodes) and the amplitude of beta oscillations (15- 25 Hz) in left motor electrodes (C3 and surrounding electrodes). The instantaneous phase and amplitude of these oscillations will be calculated by averaging the signal in these two regions of interest, band-filtering the signal to the specified range, and then performing the Hilbert transform on the signal. Phase-amplitude coupling (PAC) is then calculated by creating a hybrid signal using the amplitude of beta oscillations in left motor electrodes and the phase of delta oscillations in prefrontal electrodes:

[†][1] www.consort-statement.org , [2] www.strobe-statement.org, [3] www.icmje.org

^[4] Wasserstein RL, et al. (2016), The ASA's Statement on p-Values, *The American Statistician*, 70:2, 129-133.

^[5] Wasserstein RL, et al. (2019), Moving to a World Beyond p < 0.05, *The American Statistician*, 73:sup1, 1-19.

^[6] Amrhein, et al. (2019), Scientists rise up against statistical significance, *Nature* 567, 305-307.

^[7] Editorial (2019) It's time to talk about ditching statistical significance: ... *Nature* 567, 283-283.

$$PAC = \left| \frac{\sum_{t=1}^{N} M * e^{i\theta}}{N} \right|$$

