 $PAC = \left| \frac{\sum_{t=1}^{N} M * e^{i\theta}}{N} \right|$ M is magnitude of beta oscillations, θ is angle of delta oscillations, N is number of time points

The PAC value is normalized by creating a null distribution by randomly shifting the beta timeseries by at least 10% of the number of time points. Then, PAC is calculated between the delta-phase timeseries and each of these randomly shifted beta-amplitude timeseries. Finally, PACZ is calculated as the z-transformed true PAC value relative to the null distribution.

A two-way analysis of variance (ANOVA) will be performed using within-participant factor of time (before or after treatment) and between-participant factor stimulation type (delta-beta tACS, active-sham). We hypothesize to find an interaction between time and stimulation type. Post hoc differences will be investigated. We hypothesize that the predicted interaction will be driven by an increase in delta-beta coupling for delta-beta tACS compared to the active-sham. Sensitivity analyses will be conducted to evaluate the specificity of these effects: a similar analysis with theta-gamma coupling as the dependent variable and we do not expect that delta-beta tACS will have any effect on theta-gamma coupling.

Further, we will conduct exploratory generalized linear mixed models will be conducted to examine potential confounds on treatment effect (e.g., age, sex, baseline depressive symptoms).

Plans for Aim 3 (SECONDARY).

Goal-directed behavior will be calculated as the average decision to perform the HARD task across blocks. A two-way analysis of variance (ANOVA) will be performed using within-participant factor of time (before or after treatment) and between-participant factor stimulation type (delta-beta tACS, active-sham). We hypothesize to find an interaction between time and stimulation type. Post hoc differences will be investigated. We hypothesize that the predicted interaction will be driven by an increase in goal-directed behavior for delta-beta tACS compared to the active-sham. Sensitivity analyses will be conducted to evaluate the specificity of these effects: a similar analysis with reward-evaluation as the dependent variable and we do not expect that delta-beta tACS will have any effect on rewardevaluation.

Further, we will conduct exploratory generalized linear mixed models will be conducted to examine potential confounds on treatment effect (e.g., age, sex, baseline depressive symptoms).

Plans for Aim 4 (EXPLORATORY).

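### PACZ, the delta-beta coupling outcome, grows with the amount of EEG analysed, and section 8.3 does not hold that amount fixed

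*Combined protocol and SAP*

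**What the plan says.** Section 8.3 of the combined protocol and SAP, under Plans for Aim 2, takes the "phase of delta oscillations (2-3 Hz) in prefrontal electrodes" and the "amplitude of beta oscillations (15- 25 Hz) in left motor electrodes". The signals are obtained by "averaging the signal in these two regions of interest, band-filtering the signal to the specified range, and then performing the Hilbert transform". PAC is the modulus of the mean of M·exp(iθ) over the record, where "M is magnitude of beta oscillations, θ is angle of delta oscillations, N is number of time points". A null distribution comes from "randomly shifting the beta timeseries by at least 10% of the number of time points", and then "PACZ is calculated as the z-transformed true PAC value relative to the null distribution". PACZ goes into a two-way ANOVA of time by stimulation type, and the hypothesis is that the interaction reflects a rise in coupling under delta-beta tACS. Theta-gamma coupling is analysed in a similar way as a specificity check.

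The plan gives no recording length, epoch length, artefact-rejection rule, minimum usable EEG, number of shifts, or rule for equalising record length across visits and participants. The covariates named as examples in 8.3 are age, sex and baseline depressive symptoms. Section 8.1 allows further covariates and treats incomplete data only in general terms.

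**The concern.** The hypothesis is about the strength of coupling. A z-score against shifts of the same record measures how much evidence that record holds for coupling, and a longer record holds more evidence at the same strength. Two participants with identical coupling, or one participant at two visits, will have different PACZ values if one record has more clean EEG.

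At the least this adds noise to a comparison of 20 per arm. At worst, if the amount of usable EEG changes between visits differently in the two arms, a time-by-stimulation effect could appear, or be hidden, with no change in coupling.

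**Working it through.** **Inputs from the documents.** The frequency bands, the PAC formula, the shift of at least 10%, the z-score and the time-by-stimulation ANOVA (8.3); 20 per arm (synopsis and 5.1); threshold 0.05 (8.1), taken as two-sided. The plan states no PACZ figure, so there is none to reproduce.

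**Algebra.** Read PACZ as (PAC − m0)/s0, with m0 and s0 the mean and SD of the shifted values. For fixed non-zero coupling PAC tends to a constant. Both m0 and s0 fall as about 1/√N. So PACZ ≈ a·√N − b, with b = m0/s0 roughly constant. Doubling the record should multiply PACZ by about √2 = 1.41, and losing 25% should multiply it by about √0.75 = 0.87. The subtraction of b makes both changes somewhat larger when PACZ is small.

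**Simulation of the stated method.** Assumptions not in the documents: 1/f noise for delta; beta amplitude modulated by delta phase at depth c; 64 Hz sampling; one continuous record per visit; 200 circular shifts; 80 runs per cell.

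| Depth c | 300 s | 450 s | 600 s | 1200 s |
|---|---|---|---|---|
| 0 | 0.01 | 0.24 | 0.09 | −0.05 |
| 0.05 | 2.88 | 4.09 | 5.07 | 7.40 |
| 0.1 | 7.56 | 9.55 | 11.52 | 16.30 |
| 0.2 | 15.55 | 19.19 | 22.38 | 32.58 |

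The cells are mean PACZ. Raw PAC at c = 0.1 stayed at 0.048–0.050. With coupling present, going from 600 to 1200 s multiplied PACZ by 1.41–1.46, and going from 600 to 450 s multiplied it by 0.81–0.86. With no coupling PACZ did not move. A separate simulation with 300 shifts and 300 runs per cell gave the same pattern at weak coupling: 4.25, 6.67 and 10.16 at 5, 10 and 20 minutes.

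**Effect on the planned test.** In a 2×2 design the interaction is a t test on change scores. With 20 per arm, c = 0.1 (PACZ about 11.5) and no true effect, the false-positive rates were:

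- equal EEG everywhere: 5.3%
- 25% loss at follow-up in both arms: 4.3%, with PACZ falling by about 1.8 in each arm
- 25% less in one arm at both visits: 5.2%
- loss in one arm at follow-up only, of 10% / 25% / 50%: 13.3% / 53.1% / 99.6%

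For smaller typical PACZ values, take the shift as PACZ × (1 − √(1 − loss)) and use the noncentral t with SD of change 2.0. This SD fits the run-to-run SD of 1.41 at c = 0.05 and 600 s, since 1.41 × √2 = 1.99.

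| Typical PACZ | Shift, 25% loss | False positives, 25% | False positives, 50% |
|---|---|---|---|
| 2 | 0.27 | 7.0% | 14.7% |
| 3 | 0.40 | 9.5% | 27.3% |
| 5 | 0.67 | 17.8% | 61.7% |

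At PACZ 5 and 25% loss, the rate runs from 28.0% with SD 1.5 to 13.1% with SD 2.5. The square-root rule is on the low side here: the simulated fall at c = 0.05 was 5.07 − 4.09 = 0.98, against 5.07 × 0.134 = 0.68.

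**Noise.** If usable length had a coefficient of variation of 15–25% (assumed), PACZ would gain one of about 7.5–12.5%. On a mean of 6.67 and SD of 1.57 (10 minutes, weak coupling), the added SD is 0.50–0.83. The total SD becomes √(1.57² + 0.50²) = 1.65 to √(1.57² + 0.83²) = 1.78, a rise of about 5–13%.

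**After the fix.** Averaging PACZ over fixed 60 s segments gave 2.56, 2.49 and 2.51 at 300, 600 and 1200 s for c = 0.1, and 6.07, 5.81 and 5.99 for c = 0.2. The dependence on length is gone.

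**The case against.** A reader might infer that any inequality in EEG between visits or between arms biases the planned test. It does not. Loss that is equal in both arms at one visit moves the time main effect, and a constant arm difference moves the arm main effect. The interaction stays at its nominal rate in both cases. Allocation is randomised and double-blind (5.6, 5.7), and the analysed EEG is recorded at baseline and about two weeks after the single stimulation session (7.2), so artefact during stimulation cannot enter it. Differential loss would be mostly chance.

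A reader might also infer that treatment will create the bias through task choices. Under Plans for Aim 3, "Goal-directed behavior will be calculated as the average decision to perform the HARD task across blocks", and tACS is expected to raise it. More HARD choices would change the amount of EEG only if HARD and easy trials differ in length and the whole task record is analysed. The documents state neither, so this route is possible but not shown.

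The sizes rest on assumed record lengths and coupling depths, and the simulated SDs leave out true variation between people and visits. Real variation would lower the false-positive rates and the relative noise. This stands.

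The theta-gamma analysis would tend to show a length artefact too, but only if theta-gamma coupling is itself non-zero. If it is near zero, its PACZ stays flat, and a length artefact in delta-beta would look specific.

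The missing upper limit on the shift might be read as a second serious defect. That needs a circular, one-directional shift, which the plan does not state. On 10-minute records a 90% cap changed PACZ by 0–7%. Larger changes (22–48%) arose only on 2–30 s segments with strong coupling.

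What survives is the property of the metric. Followed as written on a whole record, PACZ depends on record length, and the plan neither fixes the length nor adjusts for it.

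**Conclusion.** The concern holds in a limited form. Whenever coupling is non-zero, PACZ as defined rises roughly with the square root of the number of time points, so it combines coupling strength with the amount of usable EEG. This follows from the formula and does not depend on the simulation settings, provided one record of varying length is analysed per visit.

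The certain consequences are noise and PACZ values that are not comparable across visits or participants. Bias in the time-by-stimulation test needs data loss that differs by arm and visit together. If that occurs, the distortion is small at PACZ of about 2 with modest loss and large at PACZ of 5 or more with heavy loss. The documents give neither typical PACZ nor usable EEG length, so the actual size cannot be stated. The point concerns a secondary mechanistic outcome and leaves the HDRS analysis untouched. It should be corrected, but it does not invalidate the aim.

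**What to change.** In 8.3, Plans for Aim 2:

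- Compute PAC and its shifted null on contiguous segments of one fixed length, set blind to arm, and average PACZ over segments for each participant and visit. Alternatively, use the same contiguous number of clean time points for everyone. Scattered time points will not do, because they break the autocorrelation on which the shift null relies.
- State a minimum usable length and the number of shifts.
- As a minor clarification, if shifts are circular, require at least 10% displacement in either direction (10–90% of the segment). This matters more as segments get shorter.
- Apply the same rules to theta-gamma coupling.
- Report usable minutes by arm and visit.

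The cost is a few lines of text and code, with no new data. Some EEG is discarded and absolute PACZ values become smaller: in the simulation at c = 0.1, about 2.5 with 60 s segments against 11.52 on a whole 600 s record. Fixed segments are preferable to cutting every record to the shortest one. On the separate weak-coupling simulation, a cut from 20 to 5 minutes would take PACZ from 10.16 to 4.25.

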7.2. Study Visits

Following an eligible phone screen, participants will be scheduled to come in for the first in-person visit within two weeks of the screen. At the session, participants will provide written consent to participate in the study. They will undergo clinician-administered assessments: Hamilton Depression Rating Scale (HDRS), the Snaith-Hamilton Pleasure Scale (SHAPS-C), the Mini International Neuropsychiatric Interview for DSM-5 (MINI) and the Columbia-Suicide severity Rating Scale (C-SSRS). Exclusion criteria for severe SUD, AN, or current psychotic symptoms will be determined from the MINI. In addition, the participant must not have suicide intent as determined by the C-SSRS. At this visit, participants will also complete a reward-related decision-making task (S-EEfRT) during EEG collection. Participants will also complete self-report questionnaires on psychological symptoms.

At the intervention visit, which will occur within one week of the baseline visit, all participants will complete a single-session 90-minute BA treatment. During the second half of the intervention visit, stimulation will occur for a duration of 30 minutes. Participants will be randomized to receive either delta-beta tACS or an active sham stimulation. The C-SSRS will also be administered.

The third session occurs approximately two weeks after the intervention session. At the session, the HDRS, SHAPS-C and C-SSRS will be administered. Participants will complete a behavioral task while EEG data are collected and self-report questionnaires on psychological symptoms.

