8.1. Strategies that Apply to all the Aims

All testing described below assumes a significance threshold of p = 0.05. Analyses will be deemed to be statistically significant if the p-value is less than this threshold. An analysis that does not exceed this threshold will be considered inconclusive.

There may be additional covariates included in the analysis. Data will be assessed for normality and, if deemed necessary, corrective procedures will be applied (e.g., log normalization). Based on our previous dataset, we expect that the variables used here will be approximately Gaussian. However, if the distribution of a variable displays a skewed tail and a test for normality fails, then it is justified to use a corrective procedure. This correction will be applied upon consideration of the variables themselves, and not based on the result of the intended analysis.

Human studies are prone to drop-out, missing data, and interval-censored values. The reasons for drop outs, missing / censored data values, and protocol departures will be documented in the database. Best practices for dealing with incomplete data will depend on the documented causes of those occurrences.

The analysis plans will include outcome-dependent exploratory analyses to generate new hypotheses.

To help ensure replicability of the research, the analysis plans will be reviewed and finalized prior to collection of data (*a priori*). For each specific aim, the analysis plans specify detailed steps for obtaining estimates of the population parameters of interest (e.g., treatment effects) and for making inferences.

- Human studies are prone to drop-out, missing data, and interval-censored values. The reasons for drop-outs, missing / censored data values, and protocol departures will be documented in the database. Best practices for dealing with incomplete data will depend on the documented causes of those occurrences. In the analysis plans established a priori, the strategies for coping with incomplete data will be based on anticipated causes. Alternative methods for dealing with incomplete data will play important roles in the sensitivity analyses.
- All hypothesis tests yielding large p-values will be reported as being inconclusive. For all sample sizes, all hypothesis test procedures are (by design) incapable of establishing that the null hypothesis is true.

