- If p-values are computed they should be reported to several decimal places without categorizing or dichotomizing the p-value; that is, the words "significant" and "non-significant" should be avoided. The p-value should be reported and interpreted as a continuous measure indicating the availability of information against

19 September 2022

the (null) hypothesis being tested. The available amount of information against the null hypothesis is equal to the Shannon Information S-value, and the p-value = $(\frac{1}{2})^{S-value}$. Smaller p-values (larger S-values) indicate greater amounts of available information. Larger p-values indicate a lack of information; e.g., if p = 1 then the S = 0. If p = 0.03125 then S = 5 which indicates a result that is as-surprising-as observing 5 'heads' in a row when flipping a coin 5 times to test whether it is a fair coin. Due to lack of information, large p-values cannot be used to draw any conclusions as to whether the tested null hypothesis is true or false. Lack of availability of evidence of an effect is not evidence of a lack of effect.

• The proposed statistical analysis strategy acknowledges that no p-value can reveal the plausibility, presence, truth, or importance of an association or effect --which is consistent with the statements of the American Statistical Association [4,5], the recommendations in Nature [6,7], and guidance, such as the CONSORT Statement [1], STROBE Statement [2], and ICMJE guidance [3].[†]]

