Exploratory analyses are planned only if effects are seen on depressive symptoms (Aim 1). If so, we plan to explore the potential effects specific to anhedonia symptoms. Treatment response will be calculated as the change in anhedonia (SHAPS-C) scores from pre- to post-treatment. A two-way analysis of variance (ANOVA) will be performed using within-participant factor of time (before or after treatment) and between-participant factor stimulation type (delta-beta tACS, active-sham). We hypothesize to find an interaction between time and stimulation type. Post hoc differences will be investigated. We hypothesize that the predicted interaction will be driven by a decrease in anhedonia symptoms for delta-beta tACS compared to the active-sham.

Further, we will conduct exploratory generalized linear mixed models will be conducted to examine potential confounds on treatment effect (e.g., age, sex, baseline non-anhedonic depressive symptoms).

Exploratory analyses with anhedonia symptoms will not be conducted if effects for overall depressive symptoms (Aim 1) are not found.

Planned Interim Analyses

No interim analyses will be performed.

The experiment proposed here will utilize a parallel arm design, and primary analyses will use a repeated-measures ANOVA with one within-participant factor (before and after treatment) and one between-participants factor (deltabeta, placebo). With an average effect size of 0.286 partial-eta square estimated from existing literature on single session BA, we estimate that we need at least 15 participants per group to achieve 80% statistical power. Using a conservative estimate of 0.5 correlation between estimates, we still reach ~99% power with 40 participants (Figure 3). Data will be collected until we reach 40 participants. Given the similarity in stimulation methodology between the current experiment and our previous experiment (Riddle et al., 2021), we anticipate adequate levels of power for hypothesis testing with 40 participants. Moreover, other studies of combined psychotherapy and stimulation have reported similar sample sizes (Neacsiu et al., 2022).

[figure not shown]

Figure 3. Power analysis for impact of BA + tACS on depressive symptoms with ANOVA.

10. Data Capture and Database Management

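### Running the exploratory SHAPS-C analysis (Aim 4) only after an Aim 1 effect works against the trial's own anhedonia question, and the specificity checks plan no comparison of effects (minor)

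*Combined protocol and SAP*

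**What the plan says.** **Aim 4.** Section 8.3 states the condition at the start of the Aim 4 plan, "Exploratory analyses are planned only if effects are seen on depressive symptoms (Aim 1", and again at its end, "Exploratory analyses with anhedonia symptoms will not be conducted if effects for overall depressive symptoms (Aim 1) are not found". Neither sentence says what counts as an effect. The natural reading is a time-by-stimulation interaction on HDRS favouring tACS, judged by section 8.1: "All testing described below assumes a significance threshold of p = 0.05".

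The condition appears nowhere else that Aim 4 is described: not in the Synopsis (aim, outcome measure, analysis plan), section 2.1, section 3 with Table 1, or Table 2. Section 8.1 does announce follow-up of this general kind: "The analysis plans will include outcome-dependent exploratory analyses to generate new hypotheses". SHAPS-C is scheduled at baseline and at the 2-week visit whatever HDRS shows. Section 7.2 says of the later visit: "At the session, the HDRS, SHAPS-C and C-SSRS will be administered".

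**Specificity.** For Aims 1, 2 and 3, section 8.3 plans a second, separate ANOVA on a control outcome (anxiety, theta-gamma coupling and reward evaluation respectively) and expects no effect there. No test compares the target effect with the control effect. On null results section 8.1 is careful: "All hypothesis tests yielding large p-values will be reported as being inconclusive". It adds that failing to see an effect does not show that there is none.

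**The concern.** Section 2.1 asks whether treatment acts particularly on anhedonia. If it does, total HDRS may move little, and the plan would then leave SHAPS-C unanalysed although the data exist. There is also a selection effect. If HDRS and SHAPS-C changes are correlated and the true effect is modest, the trials in which SHAPS-C is reported are those where chance favoured tACS on HDRS, and part of that chance carries over to SHAPS-C.

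For specificity, one significant ANOVA and one non-significant ANOVA do not show that two effects differ. The same pattern can arise when the true effects are equal. The stake is the interpretation of exploratory and supporting results, not the primary test.

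**Working it through.** **Inputs from the documents.** 20 per arm, with at least 30 complete cases expected (15 per arm if even); threshold 0.05. The planning effect is given in the sample size paragraph: "With an average effect size of 0.286 partial-eta square estimated from existing literature on single session BA".

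**Assumptions, not in the documents.** The gate is a favourable HDRS interaction at p<0.05. Effects are in SD of the change score. The correlation r between changes on two outcomes, and all effects below the planning value, are shown as ranges. The time-by-arm interaction is tested as a two-sample t-test on change. Simulations used 200,000 trials per setting for the gate and 40,000 or more for the specificity pattern; a re-run agreed within simulation error.

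**Plan's own figure.** f² = 0.286/(1 − 0.286) = 0.401; f = 0.633; d = 2f = 1.27. With noncentrality f²N = 0.401 × 40 = 16.0 on 1 and 38 df, power is 97.4%. With 0.401 × 40 × 2/(1 + 0.5) = 21.4 it is 99.4%, which matches the stated figure of about 99%. On the change-score scale used below, the gate therefore opens in 97% of trials at the planning effect.

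**Mainly-anhedonia effect** (SHAPS-C 0.8 SD, r = 0 to 0.6). Share of trials with SHAPS-C p<0.05:

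| Per arm | HDRS effect | No gate | Gate |
|---|---|---|---|
| 20 | 0.2 SD | 69% | 6-9% |
| 20 | 0.3 SD | 69% | 11-14% |
| 15 | 0.2 SD | 56% | 4-7% |
| 15 | 0.3 SD | 56% | 7-11% |

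**Estimate reported once the gate opens** (equal true effects, 20 per arm). The expected SHAPS-C estimate is its true effect plus r times the overestimate of HDRS among gate-open trials. At 0.3 SD that overestimate is about 0.48 SD, so the reported SHAPS-C effect averages 0.3 + 0.3 × 0.48 = 0.44 at r = 0.3 and 0.3 + 0.7 × 0.48 = 0.64 at r = 0.7.

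| True effect | Gate opens | Mean reported SHAPS-C, r = 0.3 to 0.7 | 95% CI coverage |
|---|---|---|---|
| 0.3 SD | 15% | 0.44 to 0.64 | 93% to 87% |
| 0.5 SD | 34% | 0.60 to 0.73 | 95% to 93% |
| 0.8 SD | 69% | 0.85 to 0.91 | 95% to 96% |
| 1.27 SD | 97% | 1.27 to 1.28 | about 95% |

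At r = 0 there is no bias at any effect size.

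**What the gate buys.** With both outcomes null, SHAPS-C is falsely positive in 0.1% (r = 0) to 0.8% (r = 0.7) of trials, against 5% ungated. With a true HDRS effect of 0.5 SD and none on SHAPS-C, the rate is 1.9-2.4% (r = 0.3 to 0.7), against 5%.

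**Specificity pattern** (20 per arm; r = 0.3, 0.5, 0.7). Probability that anxiety is non-significant given a positive HDRS result:

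| HDRS effect | Anxiety effect equal | Anxiety effect zero | Likelihood ratio |
|---|---|---|---|
| 0.5 SD | 54%, 45%, 35% | 94%, 94%, 93% | about 1.7, 2.1, 2.7 |
| 0.8 SD | 25%, 21%, 16% | 95%, 96%, 96% | about 3.8, 4.5, 6.0 |
| 1.27 SD | 2.4%, 2.2%, 1.8% | 95%, 95%, 96% | about 39 to 55 |

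The last ratio divides by a probability near 2%, so simulation error is wider there.

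**Direct contrast.** On standardised change scores the difference between outcomes has variance 2(1 − r), so the arm difference has SE √(4(1 − r)/n). With n = 20 and t(38) = 2.024, the CI half-width is 0.76, 0.64 and 0.50 SD at r = 0.3, 0.5 and 0.7. Power for 0.5 SD versus 0 is 26%, 34% and 51% (20%, 26% and 40% at 15 per arm).

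**The case against.** The gate is a deliberate, pre-stated choice for an exploratory aim, and section 8.1 foresees outcome-dependent exploration. Following up anhedonia once depression has responded is a coherent question. In a plan without multiplicity adjustment, the gate also limits false positives. All of this stands, so it would be wrong to infer that the gate does nothing except make reporting selective.

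A reader might also infer that section 8.3 contradicts the Synopsis and tables. It does not: they omit a condition that the detailed section adds. Nor does the request in section 8.1 that "they should be reported to several decimal places without categorizing or dichotomizing the p-value" forbid a gate. It concerns how p-values are reported, and the same section sets a threshold of its own. The lack of a definition for an effect being seen or found is missing detail.

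On specificity, a reader might infer that the plan will take a null control result as proof. No passage says so, and section 8.1 calls such a result inconclusive. Nor is the pattern of a positive HDRS and a null anxiety result always weak evidence: at the planning effect it would be strong.

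Finally, the mainly-anhedonia scenario and the 87% coverage rest on assumed effects and correlations, and 87% is the worst corner shown. What remains is that the gate can leave the question in section 2.1 unanswered with data in hand, and that no comparison of effects is planned.

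**Conclusion.** A minor point and a cheap improvement; the primary analysis is unaffected. The gate costs most when the effect falls mainly on anhedonia (SHAPS-C p<0.05 in 6-14% of trials instead of about 69%, at 20 per arm) or when both true effects are modest (at 0.3 SD, reported estimates of 0.44-0.64 SD with 87-93% coverage for r = 0.3 to 0.7). It costs almost nothing at the planning effect. However, that effect comes from literature on single-session BA, which both arms receive, so a smaller tACS-versus-sham difference is plausible.

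For specificity, the weight of the planned pattern runs from slight (likelihood ratio about 1.7-2.7 at 0.5 SD) through moderate (3.8-6.0 at 0.8 SD) to strong (39-55 at 1.27 SD). Because the true effect is unknown, separate ANOVAs cannot tell the reader which of these applies. All figures other than those at the planning effect rest on assumed effects, and every between-outcome correlation is assumed.

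**What to change.** **Aim 4.** In section 8.3, delete the opening conditional sentence, the two words that link the next sentence to it, and the closing conditional sentence. Always report the SHAPS-C arm difference in change with its 95% CI, labelled exploratory and unadjusted. This matches the Synopsis, Table 1 and Table 2 as they stand. The cost is one more unadjusted exploratory result, whose false-positive rate returns to 5%.

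**Specificity.** Report the anxiety, theta-gamma and reward-evaluation effects with 95% CIs. Add a direct standardised arm-by-outcome contrast with its CI, to stand beside any specificity statement rather than be its sole permitted basis. This takes one extra model per question on data already collected. The contrast is imprecise at this sample size, as the half-widths above show, and comparing clinician-rated HDRS with a self-report anxiety scale mixes construct with rater; the report should say both.

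**Wording.** Name the anxiety score in advance, since STAI and IDAS are both collected.
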